Off-pump CABG is performed to improve cardiac blood flow without the use of a cardiopulmonary bypass machine which may provoke complications including stroke, renal failure, and blood loss. Despite potential benefits, off-pump surgery can cause complications including graft occlusion, myocardial infarction, and neurocognitive deficits. The prevalence of such complications varies widely in the literature, with some studies suggesting it ranges from 5% to 30%, influenced by patient comorbidities and surgical technique. Continuous monitoring of tissue oxygenation may reduce the incidence of such complications by enabling the early detection and correction of tissue hypoperfusion. This approach could lead to more tailored and responsive patient management during and after surgery, potentially improving postoperative outcomes and reducing the overall complication rate associated with off-pump CABG.

Objectives and Endpoints

The following text was from the original protocol registered before the start of the trial.

Primary objective

To establish whether the care guided by cerebral and somatic tissue oxygen saturation monitoring compared to usual care reduces perioperative complications in patients having off-pump coronary artery bypass grafting surgery within 30 days of randomization.

Primary outcome measure

The primary outcome is a collapsed (one or more) composite of the following complications with a Clavien-Dindo grade II or greater arising within 30 days of randomization.

- Brain complications (postoperative delirium, cognition decline, stroke);
- Cardiac complications (non-fatal cardiac arrest, myocardial injury, heart failure, new-onset symptomatic ventricular arrhythmia);
- Respiratory failure;
- Renal complications (AKI stages II and III);
- Infectious complications (surgical site infection involving deep surgical site and/or organ/space, pneumonia, laboratory confirmed bloodstream infection, infection with source uncertain, and sepsis);
- Death.

Secondary objectives

To determine whether the care guided by $SctO_2$ and $SstO_2$ monitoring reduces various complications and duration of hospitalization.

Secondary outcome measures

- Components of the primary composite

- Atrial fibrillation, assessed within postoperative 30 days
- Postoperative delirium assessed from postoperative day 1 to 5
- Postoperative cognitive decline as a continuous variable assessed before surgery and on postoperative days 5 and 30

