- A narrative will be provided to explain the implications of the sensitivity analyses findings in the context of the trial conclusions.

Subgroup Analyses

- The outcomes targeted in the subgroup analyses include all primary and secondary outcomes. Interactions between the intervention and primary outcome will be evaluated for each subgroup. Odds ratio for the primary outcome, as a function of subgroup, will be presented as a forest plot with 95% confidence intervals.
- The subgroup analyses will be based on the following variables:
 - Age (< 65 years vs. \geq 65 years)
 - Sex (male vs. female)
 - BMI (< 30 kg/m² vs. $>$ 30 kg/m²)
 - Blood component transfusion during the study period (yes vs. no)
 - Duration of surgery (< 3 hours vs. $>$ 3 hours)
 - Temperature during surgery (based on each patient's median value, $<$ 35.5 °C vs. $>$ 35.5 °C)
 - Cerebral tissue oxygen saturation (based on each patient's median value, $<$ 70% vs. $>/=$ 70%)
 - Somatic tissue oxygen saturation (based on each patient's median value, $<$ 75% vs. $>/=$ 75%)
 - Cardiac output index (based on each patient's median value, $<$ 3 L/min/m² vs. $>/=$ 3 L/min/m²)
 - Systemic vascular resistance (based on each patient's median value, $<$ 1000 dyn·s·cm⁻⁵ vs. $>/=$ 1000 dyn·s·cm⁻⁵)
 - Heart rate (based on each patient's median value, $<$ 60 bpm vs. $>/=$ 60 bpm)
 - Mean arterial pressure (based on each patient's median value, $<$ 65 mmHg vs. $>/=$ 65 mmHg)
 - End-tidal carbon dioxide (based on each patient's median value, $<$ 30 mmHg vs. $>/=$ 30 mmHg)
 - History of stroke (yes vs. no)
 - History of myocardial infarction (yes vs. no)
 - History of hypertension control (based on pre-operative measurement with the threshold of 140/90 mmHg, (yes vs. no)
 - Antihypertensive medication, (yes vs. no)
 - History of diabetes (based on the preoperative diagnosis, yes vs. no)
 - History of chronic renal disease (based on the preoperative diagnosis, yes vs. no)
 - History of chronic obstructive pulmonary disease (based on the preoperative diagnosis, yes vs. no)
 - Current cigarette smoking (yes vs. no)

Ethical Considerations

The ethical considerations were specified in the protocol registered before the start of the trial.

Quality Control and Data Management

The quality control and data management were specified in the protocol registered before the start of the trial.

Software and Programming

R software (version 4.3.2, R Foundation for Statistical Computing, Australia).

Tables and Figures

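### The subgroup list mixes baseline variables with ones that arise during or after the intervention, most clearly the two saturations it guides, and treats them all alike

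*SAP*

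**What the plan says.** The Subgroup Analyses section of the SAP gives one undivided list of 21 variables, to be applied to the primary and all secondary outcomes. The instruction is "Interactions between the intervention and primary outcome will be evaluated for each subgroup". This presumably means intervention by subgroup variable; no test or significance level is named. Odds ratios for the primary outcome go to a forest plot, and the description of Figure 3 presents every line as a pre-specified subgroup.

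The entries differ in timing:
- Some are explicitly preoperative. Hypertension control, for example, is "based on pre-operative measurement with the threshold of 140/90 mmHg".
- Three fall during or after surgery: "Blood component transfusion during the study period (yes vs. no", duration of surgery, and "Temperature during surgery (based on each patient's median value".
- Seven are per-patient medians with no stated window: "Cerebral tissue oxygen saturation (based on each patient's median value" (cut at 70%), "Somatic tissue oxygen saturation (based on each patient's median value" (cut at 75%), cardiac index, systemic vascular resistance, heart rate, mean arterial pressure and end-tidal carbon dioxide.
- "Antihypertensive medication, (yes vs. no" has no time point either.

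No sentence separates these kinds or adds a caution. Elsewhere, the primary objective describes care guided by the two saturations. The opening paragraph says that monitoring may reduce complications "by enabling the early detection and correction of tissue hypoperfusion". Analysis Populations judges whether an intervention patient received the intended care by NIRS readings relative to baseline.

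**The concern.** A treatment-by-subgroup comparison is protected by randomisation only if stratum membership could not have been altered by treatment. Splitting on on-treatment saturation splits on what the intervention is meant to change. Suppose guided care moves some patients from below 70% to above it. The treated patients left below are then a different selection from the controls below, and the treated group above contains patients whose control counterparts sit below. If saturation and complications share causes such as frailty, the within-stratum odds ratios can depart from the truth even when treatment does nothing. Under some mechanisms the interaction is distorted too. Transfusion over the study period carries a further risk, because it may follow a complication that the outcome counts.

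Figure 3 would show such rows as ordinary effect modification beside valid baseline subgroups. Three row names reveal their timing; the seven medians do not.

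**Working it through.** **Classification.** The SAP gives no figure to reproduce here, so the first step is a count.

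| Timing | Variables | Number |
|---|---|---|
| During or after surgery by wording or nature | transfusion, duration of surgery, temperature | 3 |
| Per-patient median, window not stated | cerebral and somatic saturation, cardiac index, systemic vascular resistance, heart rate, mean arterial pressure, end-tidal CO2 | 7 |
| Taken as baseline | age, sex, BMI, stroke, myocardial infarction, hypertension control, antihypertensive medication (undated), diabetes, renal disease, COPD, smoking | 11 |

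3 + 7 + 11 = 21.

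**Reading the seven medians.** On-treatment monitoring is an inference, with three supports. Temperature uses the same per-patient median wording for an intraoperative value. Several entries meant as preoperative (hypertension control, diabetes, renal disease, COPD) say so. A median implies serial readings, whereas Analysis Populations refers to the NIRS starting point as a baseline value.

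**How large could the distortion be?** The SAP gives no inputs for this, so the figures below are illustrations and not bounds. Every run has no treatment effect (true odds ratio 1.00), an event rate of 30%, 4,000,000 patients, and an unmeasured frailty U ~ N(0,1) with an outcome log-odds slope of 0.4 or 0.7. Simulation error is about 0.005.

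In all but the two own-baseline rows, saturation = 67 or 70 - 3U + N(0, SD 4). In the own-baseline rows, baseline = 70 - 2U + N(0, SD 4), the on-treatment value relative to baseline = 1 - (0.03 or 0.06)U + N(0, SD 0.06), and 50%, 80% or 100% of treated patients outside 90-110% are corrected. The cut-off is 70 throughout.

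| Assumed effect of guided care on saturation | OR below 70 | OR 70 or above | Ratio high/low |
|---|---|---|---|
| None | 0.999 to 1.001 | 0.995 to 0.999 | about 1.00 |
| Correction to the edge of the patient's own band | 0.996 to 1.003 | 0.994 to 1.001 | 0.991 to 1.005 |
| Correction to the patient's own baseline | 0.931 to 0.994 | 1.006 to 1.099 | 1.012 to 1.180 |
| Uniform rise of 1 to 4 points | 1.024 to 1.246 | 1.026 to 1.248 | 0.955 to 1.046 |
| 25% or 50% of low patients lifted to 70.5 | 0.998 to 1.002 | 1.080 to 1.494 | 1.079 to 1.494 |
| Lift favouring less frail patients, probability expit(-0.7U) | 1.085 to 1.163 | 1.081 to 1.313 | 0.996 to 1.129 |

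For transfusion, the base rate is 20% or 40% and the log-odds slope on U is 0.4 or 0.7.

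| Post-complication transfusion | Intervention's effect on transfusion | OR in the transfused |
|---|---|---|
| 15% of complications | none | 0.996 to 1.003 |
| 15% of complications | lowered by 5 to 10 points | 1.050 to 1.461 |
| 15% of complications | raised by 5 to 10 points | 0.829 to 0.961 |
| none | lowered | 1.004 to 1.057 |
| none | raised | 0.954 to 0.997 |

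**Scale.** With the planned 980 per group split evenly, a stratum has 490 per arm. At a 30% event rate, p(1 - p) = 0.21, and the standard error of the log odds ratio is sqrt(2 / (490 × 0.21)) = 0.139. The 95% confidence interval then extends by a factor of exp(1.96 × 0.139) = 1.31 either way.

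**The case against.** The strongest reply has four parts.

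1. **Window.** Seven of the ten variables, including both saturations, have no stated window, and a protocol not shown here may define it. Temperature is marked as intraoperative and the medians are not, which can be read either way. This stands as a limit on certainty. On-treatment readings remain the natural interpretation, and if it is wrong, stating the window resolves the point.
2. **Mechanism.** The SAP ties the intervention only to the saturations. Nothing in it shows that monitoring changes temperature or duration of surgery, and a later variable that treatment leaves unchanged does no harm, as the zero-shift runs show. A link from complications to transfusion is likewise harmless in the null runs unless treatment also changes transfusion. This stands: the case is clear for the saturations, plausible for transfusion and conditional for the other seven. The null runs do not cover a treatment that lowers complications and thereby transfusion.
3. **Size.** The scenario nearest the SAP's adherence rule, correction to the band edge, gives almost no bias, and full return to baseline stays well inside the 1.31 factor. The largest figures need inputs that are not in the SAP. This also stands, and it is why no size is claimed.
4. **Remedy.** A label might suffice, and removing pre-specified subgroups after recruitment has closed could look selective. That is fair, but moving the rows to a separate, labelled analysis withholds nothing.

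**Conclusion.** The concern holds and should be fixed. As written, the plan gives up to ten variables that may be affected by treatment the same analysis and display as eleven baseline variables, without a caveat. The fault is clearest for the two saturations, on the reading that their medians are on-treatment values. It extends to transfusion if the intervention changes transfusion, and to the other seven only so far as the intervention changes them. The size and direction of any bias cannot be determined from the SAP; the simulated range runs from none to material and depends wholly on assumed mechanisms. No decision rule rests on the subgroups, and the primary intention-to-treat analysis is untouched.

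**What to change.** - Restrict the treatment-effect subgroup analyses and Figure 3 to variables fixed before randomisation.
- Report the remaining variables by arm in Table 2, which already includes duration of surgery, or in a separate analysis labelled exploratory and non-causal.
- State the measurement window for each of the seven medians. Keep any that was meant as a pre-intervention value.
- Use pre-intervention saturation or haemodynamic values as subgroup variables only if they were recorded in both arms. The SAP mentions a NIRS baseline only for the intervention group.
- State that antihypertensive medication is the preoperative record, if it is.
- Record the date of and reason for the change, since recruitment had ended when the SAP was written.

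The cost is SAP wording and table layout, with up to ten fewer rows in Figure 3. No new data are needed, unless a pre-intervention reading in both arms is wanted and was not recorded.
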